5.4. Secondary Efficacy Endpoint(s) Analysis

Secondary efficacy endpoints will be analyzed with the primary efficacy endpoints together. See Section 5.3 for details.

5.5. Tertiary/Exploratory Endpoint(s) Analysis

None are planned.

5.6. Safety Analyses

Safety data will be analyzed for all subjects in the Safety population.

The safety endpoints are:

- Adverse event (AE)
- Serum cortisol concentrations (Part A)
- Clinical chemistry and hematology parameters (Part A) ([Appendix B](#))
- Intraocular pressure (IOP)
- Early Treatment Diabetic Retinopathy Study (ETDRS)

	Document Number: CLN.001.SAP	Version: 0
	Document Title: Clinical Study CPN-201 Statistical Analysis Plan	Page 23 of 35

- Best corrected Visual Acuity by pinhole method
- Slit-lamp biomicroscopy
 - Corneal edema
 - Ciliary flush
 - Bulbar conjunctival injection
- Dilated indirect ophthalmoscopy
 - Vitreous
 - Retina
 - Macula
 - Choroid
 - Optic nerve

See Section 7.2 of the protocol for detail about these endpoints. The analyses of these safety endpoints are described in the following sub-sections.

For all safety endpoints, the total number of subjects in the safety population and the summary statistics of all observed data will be calculated for each active dosing regimen and its matching vehicle placebo group and each visit as defined in the CRF. No imputation will be used.

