6.3. Study Visit Schedule for Rescued Subjects

Subjects who meet the criteria for rescue presented in Section 9.4 should discontinue study drug and receive rescue medication. Subjects who are rescued should continue in the study as indicated in Table 5A or Table 5B below. Note that the assessments in the check box under each visit in the Schedule of Events (Table 2A or Table 2B) with a (R) next to “X” indicates that the assessments should be performed on rescued subjects at the indicated visits. Table 5A or Table 5B provides an overview of the study visits and assessments required for rescued subjects depending on when the rescue occurs during the study. It is important to note that (i) subjects rescued on or before POD16 in Part A will be considered as having completed the study before POD28 as indicated by ‘na’ in Table 5A and (ii) subjects rescued on or before POD9 in Part B will be considered as having completed the study before POD22 as indicated by ‘na’ in Table 5B.

Table 5A: Visits for Rescued Subjects (Part A)

Time of Rescue	Protocol Defined Study Visits				
	POD4 (± 1 day)	POD8 (± 1 day)	POD15 (± 1 day)	POD22 (± 1 day)	POD28 (± 1 day)
PODs 2-5	Conduct EOT (POD22) assessments at time of rescue but no later than POD4/5	Complete POD8 assessments in Table 2A marked with an (R)	Complete EOS (POD28) assessments and terminate subject from the study	na	na
PODs 6-9	per protocol	Conduct EOT (POD22) assessments at time of rescue but no later than POD7/8/9	Complete EOS (POD28) assessments and terminate subject from the study	na	na
PODs 10-16	per protocol	per protocol	Conduct EOT (POD22) assessments at time of rescue but no later than POD14/15/16	Complete EOS (POD28) assessments and terminate subject from the study	na
PODs 17-22	per protocol	per protocol	per protocol	Complete EOT (POD22) assessments at time of rescue but no later than POD22/23	Complete EOS (POD28) assessments and termination subject from the study

na = not applicable

Table 5B: Visits for Rescued Subjects (Part B)

Time of Rescue	Protocol Defined Study Visits			
	POD4 (± 1 day)	POD8 (± 1 day)	POD15 (± 1 day)	POD22 (± 1 day)
PODs 2-5	Conduct EOT (POD15) assessments at time of rescue but no later than POD4/5	Complete POD8 assessments in Table 2B marked with an (R)	Complete EOS (POD22) assessments and terminate subject from the study	na

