PODs 6-9	per protocol	Conduct EOT (POD15) assessments at time of rescue but no later than POD7/8/9	Complete EOS (POD22) assessments and terminate subject from the study	na
PODs 10-16	per protocol	per protocol	Conduct EOT (POD15) assessments at time of rescue but no later than POD15/16	Complete EOS (POD22) assessments and terminate subject from the study

na = not applicable

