APPENDIX A: LABORATORY EVALUATION PARAMETERS

Part A ONLY: Clinical chemistry and hematology parameters. Venous blood samples will be drawn at POD1 (pre-dose of study drug), POD22 (or EOT visit) and at the EOS visit. If a subject withdraws from study early (early termination) or is rescued prior to POD22, then the venous blood samples will be drawn on the day that the subject discontinues the study drug (EOT), or as soon as possible after that.

Parameters to be tested are listed below:

Hematology

Platelet Count	RBC Indices:
RBC Count	MCV
Absolute WBC Count (absolute) and automated differential WBC count	MCH
Hemoglobin	MCHC

Clinical Chemistry

Glucose	Chloride	Sodium	ALT (alanine amino transferase)
Calcium	BUN (blood urea nitrogen)	Potassium	AST (aspartate amino transferase)
Albumin	Creatinine	CO ₂	Bilirubin
Total protein	ALP (alkaline phosphatase)		
Cortisol - Blood drawn on POD 1/pre-Randomization and on POD22/EOT.

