5.1.5. Visits, Days, PODs, EOT and EOS

5.1.5.1. Definition of Visits

Based on [Tables C1 and C2](#), Schedule of Events, visits and their nominal days relative to the surgery are further described in [Table E](#) below.

	Document Number: CLN.001.SAP	Version: 0
	Document Title: Clinical Study CPN-201 Statistical Analysis Plan	Page 14 of 35

Table E: Visits

Visit Number	Visit Name	Notes
10	Screening	Days -28 to -1. Baseline for most safety endpoints
20	Surgery	Day 0
30	POD1	Randomization and start of study drug. Baseline for efficacy endpoints
40	POD4	3-5 days post-surgery
50	POD8	7-9 days post-surgery
60	POD15 (Part A only)	14 -16 days post-surgery for Part A
70	End of Treatment (EOT) POD22 (Part A) POD15 (Part B)	1-2 days post last dose of study drug. Part A: 22-23 days post-surgery Part B: 15-16 days post-surgery
80	End of Study (EOS) POD28 (Part A) POD22 (Part B)	6-8 days post the last dose of study drug. Part A: 27-29 days post-surgery. Part B: 20-22 days post-surgery
90	UNSCHEDULED	

Some subjects may discontinue their study drug before the scheduled EOT. Situations like this will be discussed in the following sections.

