5.1.5.2 Visit windows

It is expected that all visits should occur according to the protocol schedule described in [Table C1](#) and [Table C2](#), the Schedule of Events; visits outside of this schedule will be addressed as protocol deviations. A new visit variable, AVISIT, will be defined based on the visit date relative to the date of surgery and a windowing strategy described by [Table F](#). AVISIT will only be used for efficacy variables.

Table F: Windowing Strategy:

Surgery	Day 1 post-surgery	2-6 days post-surgery	7-11 days post-surgery	12-18 days post-surgery	19-25 days post-surgery	26+ days post-surgery
Day 0	POD1	POD4	POD8	POD15	POD22	POD28

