5.6.4. Serum Cortisol Concentration (Part A only)

Serum cortisol concentration will be summarized in the same way as other laboratory tests for POD1 pre-randomization and EOT for the active and its matching vehicle placebo groups in Part A in [Table 14.3.5.3](#) and [14.3.5.4](#) and visually presented in [Figures 14.3.5.1](#).

All serum cortisol values and their flags (H or L) defined by Covance Laboratory Services will be listed for all subjects by treatment for Screening and EOT visits in [Listing 16.2.8.4](#). All individual subject values will be visually presented in [Figure 14.3.5.2](#).

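### Part A laboratory and cortisol results share one EOT column that can hold draws from about POD2 to POD23, and the SAP gives conflicting visit rules for slit-lamp signs

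*SAP*

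**What the plan says.** **Visit basis.** SAP 5.6 summarizes safety endpoints "for each active dosing regimen and its matching vehicle placebo group and each visit as defined in the CRF", without imputation. SAP 5.1.5.2 defines date windows (Table F) but adds that "AVISIT will only be used for efficacy variables".

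**When EOT happens.** SAP Table E schedules it as "Part A: 22-23 days post-surgery" and "Part B: 15-16 days post-surgery". For a Part A subject rescued on PODs 2-5, Protocol Table 5A says "Conduct EOT (POD22) assessments at time of rescue but no later than POD4/5". Table 5B follows the same pattern in Part B; its last row reads "Conduct EOT (POD15) assessments at time of rescue but no later than POD15/16".

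**Blood draws (Part A only).** For rescue or early withdrawal before POD22, Protocol Appendix A says "then the venous blood samples will be drawn on the day that the subject discontinues the study drug (EOT"), or as soon as possible afterwards. SAP Appendix B uses the EOT label for both groups too.

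**Tables.** SAP 5.6.3 reports laboratory values at POD1 pre-dose, EOT and EOS. SAP 5.6.4 says "Serum cortisol concentration will be summarized in the same way as other laboratory tests for POD1 pre-randomization and EOT". Slit-lamp signs (SAP 5.6.7) are tabulated by visit. SAP 5.1.9, however, tells the programmer to take, for a categorical safety endpoint, the latest assessment inside the post-operative-day window.

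**The concern.** EOT means two things: a calendar time (day 22 in Part A) and the moment dosing ends. For efficacy, SAP 5.1.6.2 removes the ambiguity by replacing EOT with POD22 or POD15. For laboratory and cortisol data nothing equivalent is done.

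Cortisol is drawn only at POD1 and EOT, so this one column carries the whole post-baseline cortisol result. A subject rescued on POD4 has had about 3 days of drug and would be averaged with subjects dosed for 21 days. If early stopping is more common on vehicle, the two arms' EOT values would also come from different times after surgery.

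For slit-lamp signs the stake is different. Two programmers following different sections of the same SAP would build different tables. Under the CRF-visit reading, early post-surgical signs would sit in the EOT column.

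**Working it through.** The plan states no figure for this point, so there is none to reproduce. The check traces the label and then sizes the mixing.

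**1. Span of the EOT column**
- Part A: the earliest rescue row starts at POD2 (Table 5A) and the scheduled window ends at day 23 (Table E). 23 - 2 + 1 = 22 days, against a scheduled window of 2 days.
- Part B (slit-lamp signs only, because no blood is drawn): 16 - 2 + 1 = 15 days, against 2.
- Table F windows are POD4 = days 2-6, POD8 = 7-11, POD15 = 12-18 and POD22 = 19-25. Under these no column spans more than 7 days.
- Exposure: dosing starts on POD1, so stopping on POD2 gives about 1 day, and completing Part A gives 21.

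**2. Timing by arm, Part A (assumed rescue rates and days)**

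Mean EOT day = (1 - r) × 22 + r × m, where r is the share rescued and m the mean rescue day.

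| r active / vehicle | m | Active | Vehicle | Gap (days) |
|---|---|---|---|---|
| 10% / 10% | 8 | 20.6 | 20.6 | 0 |
| 5% / 20% | 8 | 21.3 | 19.2 | 2.1 |
| 10% / 40% | 8 | 20.6 | 16.4 | 4.2 |
| 10% / 60% | 8 | 20.6 | 13.6 | 7.0 |
| 10% / 40% | 4 | 20.2 | 14.8 | 5.4 |
| 10% / 40% | 12 | 21.0 | 18.0 | 3.0 |

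**3. Cortisol in the active arm**

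With 10% early stops, 0.10 × 21 = 2.1, or about 2 of 21 subjects. Take the extreme assumption that they show no cortisol effect at all. The arm mean then shows 19/21 = 0.90 of the 21-day effect. The dilution is modest unless active subjects stop early more often.

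**4. Slit-lamp signs, only if the CRF-visit reading is applied**

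Assume corneal edema prevalence is 40% at an early stop and 5% at scheduled EOT in both arms, with no drug effect. EOT prevalence = s × 0.40 + (1 - s) × 0.05, where s is the share stopping early. The difference between arms is therefore (s vehicle - s active) × 0.35.
- 20% versus 5%: 0.15 × 0.35 = 5.25 points.
- 40% versus 10%: 19% versus 8.5%, or 10.5 points.
- 50% versus 15%: 0.35 × 0.35 = 12.25 points.
- Equal in number and timing: 0.

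**5. Which tables are affected**
- Laboratory values and cortisol: single EOT column, no rule separating early from scheduled draws. Affected.
- Slit-lamp signs: 5.6 and 5.1.5.2 point to CRF visits, 5.1.9 to POD windows. Unresolved.
- Study-eye IOP: 5.6.5 refers to the observed-data method of 5.3.2, which is on-drug and uses Table F. Not affected.
- Visual-acuity worsening: tabulated by POD in 5.6.6. Not affected.
- Ophthalmoscopy and lens findings: Screening and EOS only, so there is no EOT column.

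**The case against.** A sample taken when dosing stops is a valid end-of-exposure measure, and Table E itself ties EOT to the last dose. Cortisol values are listed and plotted individually, and dosing diaries and rescue details are listed, so a careful reader could reconstruct the timing. The study is exploratory, and no laboratory or cortisol test is planned. All of this stands. It limits the harm but leaves the summary table without any sign of how long subjects had been dosed.

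A reader might infer more than the documents support:
- **That safety tables in general pool early and late EOT.** IOP and visual-acuity worsening are specified by POD.
- **That slit-lamp signs are pooled.** SAP 5.1.9 has a specific rule that would put a rescue-day examination in its own window, and 5.1.7 places the study-eye POD examinations in one table. What is established is a contradiction. Which CRF page holds a rescue-day examination is also unknown, because the CRF is not among the documents.
- **That timing differs by arm.** This is plausible, since rescue is triggered by uncontrolled cells or flare, but it remains an inference without rescue rates.
- **That cortisol is the only check on the HPA axis.** It is the only laboratory one; Protocol Table 3 also calls for monitoring of symptoms and signs.

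A further caution applies to the remedy. Comparing arms only on scheduled draws would compare subsets selected after randomization, possibly differently by arm.

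**Conclusion.** The point holds for Part A laboratory values and cortisol. Their single EOT column can span 22 days (about 1 to 21 days of exposure) instead of 2, and no SAP rule separates early from scheduled draws. The span follows from the documents. Any difference between arms rests on assumed rescue: 2.1 to 7.0 days for the unequal rates tried at a mean rescue day of 8, and zero if rescue is equal in number and timing.

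For slit-lamp signs the supported conclusion is that SAP 5.1.9 disagrees with 5.1.5.2 and 5.6 and must be reconciled with them. The 5.25 to 12.25 points for corneal edema are illustrative and arise only under the CRF-visit reading and the assumed prevalences and stopping rates.

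**What to change.** 1. In SAP 5.6.3 and 5.6.4, keep the all-subject EOT row. Add a scheduled EOT row (days 19-25) and an early EOT row (before day 19), each with days of exposure. Describe the scheduled row as on-treatment completers, and do not make it the sole arm comparison. A rescue on days 19-22 would fall in that row, which is one reason to show exposure.
2. Amend SAP 5.1.5.2 and 5.6 to agree with 5.1.9, so that slit-lamp signs are tabulated by Table F windows and each rescue-day EOT falls in its own window.

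The cost is SAP wording and some programming; the visit dates are already needed for Table F. The downside is small rows: at the assumed 10%, the early row on active would hold about 2 subjects. If tables have already been produced, the extra rows can be added as supplementary output and recorded under SAP 5.1.11.

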5.6.1. Extent of Exposure

The summary statistics of number of eye drops that were instilled correctly in the study eye during the entire treatment course will be calculated for each active dosing regimen and its matching vehicle placebo group and will be presented in [Table 14.1.4](#). Individual dosing diary will be presented in [Listing 16.2.5.1](#)

5.6.2. Adverse Events

Adverse events (AE) will be summarized by total number of any AE, number of subjects reporting the AE, ocular AEs (affecting the study eye and/or the non-study eye and/or both eyes, when appropriate), systemic AEs, SAEs, discontinuing study drug due to an AE, by relationship to study drug only, to ocular surgery only, or to both drug and ocular surgery, and by severity. Adverse events will be coded using Medical Dictionary for Regulatory Activities (MedDRA version 22.0 – March 2019) and categorized by system organ class and preferred terms.

See [Tables 14.3.1.1 – 14.3.1.3](#) for details.

All adverse events will be listed by both reported term and MedDRA term in [Listing 16.2.7.1](#) and [16.2.7.2](#).

	Document Number: CLN.001.SAP	Version: 0
	Document Title: Clinical Study CPN-201 Statistical Analysis Plan	Page 24 of 35

All serious and significant adverse events will be listed in [Table 14.3.2](#) and narrated in [Table 14.3.3](#).

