- Medications routinely administered prior to and following cataract surgery will be recorded in the source documents and as concomitant medications (ConMeds) in eCRF. These medications will be indicated for routine cataract surgery and should not be associated with treatment for AEs. If a medication is administered due to an AE, the medication (and AE) must be entered on the appropriate pages of the eCRF. NOTE: Acetaminophen may be administered as needed pre and post-operatively on the day of surgery.
- AEs and ConMeds should only be recorded on Day 0 if they result in disqualification (i.e., screen failure) of the subject; otherwise, the AEs and ConMeds applicable to Day 0 should be recorded on POD1 when the subject returns at the POD1 visit.
- Schedule the subject to return to the clinic on the following day POD1 in the morning (as much as possible).

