8. ADVERSE EVENTS

8.1. Definition of Adverse Events (AEs)

Adverse event means any untoward medical occurrence in a subject or clinical investigation subject administered a pharmaceutical product and which does not necessarily have a causal relationship with this treatment (21CFR312.32 (a); ICF E6 Section 1). An AE can therefore be any unfavorable sign and unintended sign (including an abnormal laboratory finding), symptom, or disease temporally associated with the use of a medicinal (investigational) product, whether or not related to the medicinal (investigational) product.

Note:

- *Reporting of AEs that may or may not be related to the ocular surgical procedure depends on their severity:*
 - i. *An AE that the Investigator considers to be within what is normally expected for cataract surgery will be recorded in a table in the source documents and no further reporting is required.*
 - ii. *An AE that the Investigator considers to be outside what is normally expected for cataract surgery or is associated with clinical sequelae will be recorded in the full AE page in the source documents and also in the eCRF,*
- *Rescued subjects are considered to be treatment failures, and rescue itself is not considered an AE.*
- *Adverse events occurring in rescued subjects should be reported in the eCF.*
- *An anterior chamber cell count > 30 on POD1 that leads to disqualification of the subject prior to Randomization should be reported as an AE.*
- *An IOP > 30 mmHg after Randomization should be reported as an AE.*
- *An IOP ≥ 24 mmHg AND an IOP increase ≥ 10 mmHg from pre-dose baseline should be reported as an AE.*

The term “severe” is used to describe the intensity of an AE; the event itself could be of relatively minor clinical significance (e.g., ‘severe’ headache). This is not the same as “serious”. Seriousness of AEs is based on the outcome of an AE and usually associated with events that pose a threat to a subject’s life or functioning.

A Treatment Emergent Adverse Event (TEAE) will be defined as any AE that occurs after the study drug dosing is initiated. For the purpose of this study, a TEAE may be related to the ocular surgical procedure and/or to the initiation of the study drug.

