8.7. Serious Adverse Event Reporting

8.7.1. Reporting Requirements

It is the responsibility of the Investigators or their designees to report any event of this nature to the Sponsor or a designee within 24 hours of the event being brought to the Investigators' or their staffs' attention. It is also the responsibility of the Investigator to report all SAEs reported at their site to the IRB, as required. The Investigator should make every attempt to follow all SAEs to resolution.

All SAEs have to be reported, whether or not considered causally related to the investigational drug product, or to the study procedure(s). All SAEs will be recorded in the eCRF. SAEs will be recorded from the time of informed consent.

All Serious Adverse Events (SAE) must be reported, whether or not considered related to the study drug, on a separate SAE Report Form. All SAEs will also be recorded in the eCRF. The Sponsor will be responsible for reporting all SAEs to regulatory authorities and ethics committees (see NOTE below) in accordance with ICH Good Clinical Practice and local regulations. As soon as the Investigator is aware of a potential SAE he/she should contact [REDACTED] by fax or e-mail and in any case *no later than 24 hours* after the knowledge of such a case. At the time of initial reporting the Investigator must provide as a minimum requirement, subject number, birth date, description of the SAE and a preliminary assessment of causality.

For fatal or life-threatening adverse events where important or relevant information is missing, active follow-up is undertaken immediately. Investigators or other site personnel inform the Study Medical Monitor, the Sponsor, and the CRO for Study Management and Monitoring of any follow-up information on a previously reported SAE immediately but no later than within 24 hours of when the Investigator becomes aware of it. The Study Medical Monitor or Sponsor Medical Monitor will advise the Investigator/study site personnel how to proceed.

The SAE reporting procedures are detailed in the study specific Safety Management Plan. This plan is an agreement between the Sponsor, the CRO for Study Management and Monitoring and Drug Safety Navigator.

NOTE: If an unexpected SAE occurs at any one site that is determined to be related, probably related or possibly related to study drug, all study sites will be notified by the

Sponsor via the CRO for Study Management and Monitoring and each site will report it to the IRB.

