10.3.3. Analysis of Safety

Analysis of safety data will be performed for all subjects in the Safety Population.

Adverse events (AE) will be summarized by total number of any AE, number of subjects reporting the AE, ocular AEs (affecting the study eye and/or the non-study eye and/or both eyes, when appropriate), ocular TEAEs in the study eye, systemic AEs, SAEs, suspected unexpected serious adverse reaction (SUSARs), discontinuing study drug due to an AE, by relationship to study drug and/or ocular surgical procedure, and by severity. Adverse events will be coded using Medical Dictionary for Regulatory Activities (MedDRA, most current version) and categorized by system organ class and preferred terms.

The analyses of IOP will include the summary statistics of IOP and its change from baseline (POD1/pre-dose) at each visit, the proportion of subjects with an IOP ≥ 24 mmHg AND an increase ≥ 10 mm Hg from pre-dose baseline, and the proportion of subjects with an IOP > 30 mmHg at any time following initiation of study drug.

The proportion of subjects with a visual acuity worsening from POD1/pre-dose visit of ≥ 2 lines will also be summarized.

Ocular symptoms, comfort grading assessment, ophthalmoscopy findings, and slit lamp biomicroscopy results will be categorically summarized.

Details of statistical analyses will be included in the SAP.

10.3.4. Interim Analysis:

No interim analyses are planned for this study.

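### SAP 5.6.2 leaves out, undeclared, the protocol's only treatment-emergent AE summary, so no by-arm AE table it describes is limited to onset after first dose

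*SAP*

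**What the plan says.** Protocol 8.1 defines a treatment-emergent AE: it "will be defined as any AE that occurs after the study drug dosing is initiated". Protocol 10.3.3 uses the term once. After the any-AE and ocular-AE items, its list of AE summaries continues with "ocular TEAEs in the study eye, systemic AEs, SAEs, suspected unexpected serious adverse reaction (SUSARs", then discontinuations, relationship and severity.

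SAP 5.6.2 follows that list closely. It opens with the same item (AEs "will be summarized by total number of any AE, number of subjects reporting the AE") and comes to ocular AEs "affecting the study eye and/or the non-study eye and/or both eyes, when appropriate), systemic AEs, SAEs, discontinuing study drug due to an AE". The study-eye TEAE item and the SUSAR item are gone. The readable SAP text does not define or use a TEAE.

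SAP 6.6, which lists changes to protocol-planned analyses, names only the added ACC-grade analyses. The SAP appendix makes several corrections and modifications, but none concerns TEAEs or SUSARs.

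**The concern.** Safety and tolerability against vehicle is the primary safety objective. Every subject has had surgery on the study eye the day before randomization, so that eye is where pre-dose events are most likely. The missing row is the one that would have separated study-eye events starting after dosing from those starting before it.

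An event that began before the first dose cannot be caused by study drug. If it is counted under an arm, it adds noise and brings the two arms' proportions closer together. With about 21 subjects per arm, one subject with only a pre-dose event moves an arm's AE proportion by 1/21 = 4.8 percentage points.

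**Working it through.** **Can pre-dose events reach the by-arm tables?**

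1. *Collection.* Both schedules (Protocol Tables 2A and 2B; SAP Tables C1 and C2) record AEs from Screening. For subjects who continue, Protocol 6.2.1 says "the AEs and ConMeds applicable to Day 0 should be recorded on POD1 when the subject returns at the POD1 visit". Protocol 8.7.1 adds that "SAEs will be recorded from the time of informed consent".
2. *Order on POD1.* Assessments precede randomization, and the first dose follows it (Protocol 6.2.2). Screening, Day 0 and pre-dose POD1 events therefore all fall outside the Protocol 8.1 TEAE definition.
3. *Population.* The Safety population (SAP 4.1) is everyone who received a dose. It selects subjects and does not filter events by onset.
4. *Onset rule.* SAP 5.1.6.1 completes partial AE dates so that each AE can be classed as on study drug or not. No AE summary described in 5.6.2 uses that class.

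So in the readable text nothing keeps a dosed subject's pre-dose AE out of the any-AE, ocular, systemic or SAE rows.

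**How large could the effect be?** The documents give no AE rates. The only sizing figure is 21 per arm, and it holds to rounding: 21 × 0.95 = 19.95, about 20 completers. The point does not depend on it.

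Let p be the proportion of an arm with a TEAE, and q the proportion with a recorded pre-dose AE. Take q as equal in both arms and independent of later AEs. Then:

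- any-AE proportion = 1 − (1 − p)(1 − q)
- any-AE risk difference = (1 − q) × (TEAE risk difference)

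With assumed TEAE rates of 30% active and 10% vehicle:

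| Assumed q | Active | Vehicle | Difference (points) | Ratio |
|---|---|---|---|---|
| 0 | 30.0% | 10.0% | 20.0 | 3.00 |
| 5% | 33.5% | 14.5% | 19.0 | 2.31 |
| 10% | 37.0% | 19.0% | 18.0 | 1.95 |
| 20% | 44.0% | 28.0% | 16.0 | 1.57 |
| 30% | 51.0% | 37.0% | 14.0 | 1.38 |

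For example, at q = 20%: active 1 − 0.7 × 0.8 = 0.44, vehicle 1 − 0.9 × 0.8 = 0.28.

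Other assumed TEAE rates behave the same way. For q = 5, 10, 20 and 30%:

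- 40% against 20%: the ratio falls from 2.00 to 1.79, 1.64, 1.44 and 1.32.
- 50% against 20%: the ratio falls from 2.50 to 2.19, 1.96, 1.67 and 1.48.

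Under this model the direction is certain. The ratio is more sensitive than the difference.

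**The case against.** A reader might infer that the SAP replaced a treatment-emergent safety analysis with an any-AE tabulation. The documents do not support that. Protocol 10.3.3 itself says "Adverse events (AE) will be summarized by total number of any AE, number of subjects reporting the AE", and its any-AE, systemic and SAE items carry no onset filter either. It planned one TEAE summary, for ocular study-eye events only. Summarizing all AEs by onset therefore goes beyond the protocol.

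A reader might also infer a large dilution from the lower rows of the table. No pre-dose rate in the documents supports that, and several provisions limit q or its effect:

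- Surgical AEs within what is normally expected are kept in source documents and not entered in the eCRF (Protocol 8.1).
- Subjects with surgical complications judged to confound results are ineligible (Protocol 4.2, criterion 7). Those disqualified on POD1 for a cell count above 30 are never dosed.
- SAP 5.6.2 splits AEs by relationship to drug only, surgery only or both, so an event attributed to surgery alone can be seen as such.
- Drug-related and drug-discontinuation rows are post-dose by nature, and the IOP rows in SAP 5.6.5 count events after dosing starts.
- Even at q = 20%, the 4-point loss in the difference is 0.04 × 21 = 0.84 of a subject.

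The comparison is also descriptive: there are no formal hypotheses, and 5.6.2 specifies no AE test. Pre-dose events are balanced in expectation by randomization. A TEAE may itself be surgery-related under Protocol 8.1, so an onset filter does not remove all surgical noise. SUSARs are an expedited-reporting class, and SAEs remain tabulated. Finally, the shells of Tables 14.3.1.1 to 14.3.1.3 are not visible in the text available, so a TEAE split there cannot be excluded.

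Most of this stands, and it limits the weight of the point. It does not explain why two protocol-planned items are missing and undeclared, or why the date classification in 5.1.6.1 feeds no described AE summary.

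**Conclusion.** The mismatch between protocol and SAP is established by comparing the texts and needs no assumed rates. SAP 5.6.2 omits the only planned TEAE summary and the SUSAR item, and neither SAP 6.6 nor the appendix says so. As the readable text stands, pre-dose AEs of dosed subjects can be counted in the by-arm any-AE, ocular, systemic and SAE summaries.

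The resulting attenuation is real in direction but unknown in size. It is a factor of 1 − q on the risk difference, assuming equal q in both arms and independence from later AEs. The 5% to 30% range for q and the TEAE rates used above are illustrations only, and q may be near or below the low end. No formal test is affected. This is a minor-to-moderate item that is cheap to put right.

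**What to change.** - Carry the Protocol 8.1 TEAE definition into SAP 5.6.2.
- Restore the study-eye ocular TEAE summary and the SUSAR item.
- Add by-arm AE summaries limited to onset at or after first dose, using the dates completed under 5.1.6.1. The existing any-AE rows can stay.
- Show AEs with earlier onset in a separate row or listing.
- For POD1 events, use onset time if it is collected. Neither document says that it is, so otherwise state a convention for events dated on the day of first dose. The convention will also decide events with a partial start date, because 5.1.6.1 assigns many of those to that day.
- Declare any remaining departure from Protocol 10.3.3 in SAP 6.6.

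The cost is SAP wording, an onset-date filter, a little extra programming and one convention for POD1. No new data are needed if the date convention is used.
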